8.2 Recording of Adverse Events

At each contact with the subject, the investigator will seek information on adverse events by specific questioning and, as appropriate, by examination. Information on all adverse events will be recorded immediately in the source document, and also in the appropriate adverse event module of the case report form (CRF). All clearly related signs, symptoms, and abnormal diagnostic procedures results will be recorded in the source document, grouped under one diagnosis.

All adverse events occurring during the study period will be recorded. The clinical course of each event will be followed until resolution, stabilization, or until it has been determined that the study treatment or participation is not the cause. Serious adverse events that are still ongoing at the end of the study period will be followed up to determine the final outcome. Any serious adverse event that occurs after the study period and is considered to be possibly related to the study treatment or study participation will be recorded and reported immediately.

8.3 Reporting of Serious Adverse Events and Unanticipated Problems

Investigators will conform to the adverse event reporting timelines, formats and requirements of the various entities to which they are responsible, but at a minimum those events that must be reported are those that are:

- related to study participation,
- unexpected, and
- serious or involve risks to subjects or others

If the report is supplied as a narrative, the minimum necessary information to be provided includes

Study Identifier	Current status
Study Center	Whether study treatment was discontinued
Subject number	Reason why event classified as serious
Date and description of the event	Investigator determination of association between event and treatment

Investigator reporting:

For reportable deaths, the initial submission to the UNC IRB may be made by contacting the IRB Director or Associate Director. The AE/Unanticipated Problem Form is required as a follow up to the initial submission. AEs are reported to the IRB if they are unexpected in nature, severity or frequency and related or possibly related to administration of study intervention.

Other Reportable events:

For clinical drug trials, the following events are also reportable to the UNC IRB:

- Any adverse experience that, even without detailed analysis, represents a serious unexpected adverse event that is rare in the absence of exposure (such as agranulocytosis, hepatic necrosis, Stevens-Johnson syndrome).
- Any adverse event that would cause the PI to modify the investigators brochure, protocol or informed consent form, or would prompt other action by the IRB to assure protection of human subjects.
- Information that indicates a change to the risks or potential benefits of the research, in terms of severity or frequency. For example:
 - Safety monitoring indicates that a particular side effect is more severe, or more frequent than initially expected.
 - A paper is published from another study that shows that your research study is of no therapeutic value.
- Change in FDA safety labeling or withdrawal from marketing of a drug, device, or biologic used in a research protocol.
- Breach of confidentiality
- Change to the protocol taken without prior IRB review to eliminate apparent immediate hazard to a research participant.
- Incarceration of a participant when the research was not previously approved under Subpart C and the investigator believes it is in the best interest of the subject to remain on the study.
- Complaint of a participant when the complaint indicates unexpected risks or the complaint cannot be resolved by the research team.
- Protocol violation (meaning an accidental or unintentional deviation from the IRB approved protocol) that in the opinion of the investigator placed one or more participants at increased risk, or affects the rights or welfare of subjects.

8.3.1 Sponsor reporting: Notifying the FDA

The study sponsor (in this case, the PI) is required to report certain study events in an expedited fashion to the FDA. These written notifications of adverse events are referred to as IND safety reports. The following describes the safety reporting requirements by timeline for reporting and associated type of event:

- ***Within 7 calendar days***
Any study event that is:
 - associated with the use of the study agent
 - unexpected,
 - fatal or life-threatening, and
 - ***Within 15 calendar days***
Any study event that is:
 - associated with the use of the study agent,
 - unexpected, and
 - serious, but not fatal or life-threatening
- or-

- a previous adverse event that was not initially deemed reportable but is later found to fit the criteria for reporting (reporting within 15 calendar days from when event was deemed reportable).

Any finding from tests in laboratory animals that:

- suggest a significant risk for human subjects including reports of mutagenicity, teratogenicity, or carcinogenicity.

Additional reporting requirements

Sponsors are also required to identify in IND safety reports all previous reports concerning similar adverse events and to analyze the significance of the current event in light of the previous reports.

Reporting Process

Adverse events may be submitted on FDA Form 3500A or in a narrative format. If supplied as in a narrative format, the minimum information to be supplied is noted above at the beginning of section 8.3. The contact information for submitting IND safety reports is noted below:

[name] at [contact]

8.4 Stopping Rules

The study will be stopped under the following circumstances:

- Any maternal or fetal death deemed to be related or possibly related to study participation
- >20% subjects experience liver toxicity (defined as AST or ALT \geq 3x ULN within 24 hours of study drug)

Specific rules to stop study intervention for individual subject

- Delivery, or 34 weeks, which ever occurs first
- Liver toxicity (LFTs \geq 3x ULN within 24 hours of study drug)
- Maternal side effects that cannot be managed with oral medication

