There are no proven measures to treat preeclampsia; resolution occurs only with delivery. In early onset preeclampsia ($<$ 34 weeks), delaying delivery and prolongation of pregnancy is of benefit to the fetus but potentially detrimental to the mother. Medically indicated preterm birth as a secondary result of fetal or maternal complications contributes significantly to neonatal morbidity and mortality associated with preeclampsia.¹² As shown in Figure 1, **preeclampsia is**

one of the leading causes of medically indicated preterm birth. Conservatively estimated, > 20,000 preterm births < 34 weeks occur annually in the United States due to complications of preeclampsia. A therapeutic approach to early-onset preeclampsia to prolong pregnancy that will do no harm to both the mother and fetus is an important and unmet med.

The pathophysiology of preeclampsia is complex and incompletely understood. Activation of several different pathways is thought to be operative in the development of preeclampsia. Evidence exists to support excessive maternal inflammation¹³ maternal immunologic responses¹⁴, placental hypoxia and oxidative stress¹⁵, generalized vasospasm, and alteration of growth factor production, as part of the pathophysiologic process in preeclampsia. The sentinel paper by Roberts et. al.¹⁶ implicated angiogenic imbalance with endothelial activation and generalized maternal endothelial dysfunction as the explanation for most of the clinical aspects of preeclampsia. These pathways are all believed to culminate in endothelial activation and dysfunction¹⁷, characterized by an imbalance between circulating pro- and anti-angiogenic factors.

Angiogenesis requires the complex interplay between vascular endothelial growth factor (VEGF), placental growth factor (PlGF), and their receptors, soluble fms-like tyrosine kinase-1 (sFlt-1) and VEGFR-1. The placenta is a rich source of these factors, and in addition to regulating vascular homeostasis, VEGF, PlGF, and sFlt-1 are key components in regulating trophoblast cell function and survival.¹⁸⁻²⁰ sFlt-1 acts as an anti-angiogenic factor by neutralizing PlGF and VEGF.²¹

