3.1 General Design

This is an open labeled phase II study of vitamin B₃-amide dietary supplementation in pregnant women with early-onset preeclampsia, per ACOG guidelines. We will enroll 24 pregnant women at 24-33 weeks 3 days with EOP and anticipated treatment by expectant observation. If the woman is anticipated to remain undelivered for 48 hours after diagnosis she will receive vitamin B₃-amide, 2.5 mg/day dosed in the following manner: administered as 1000mg at 8AM and 12MN; 500mg at 4PM, continuing until delivery or 34 weeks, whichever occurs first. Optional research blood samples will be collected at times of clinically indicated blood draws (baseline and 2-3 times per week) to measure nicotinamide and its metabolite 2-pyridone, sFlt-1 and PIGF. A sample of cord blood will be collected (6ml) following delivery.

All study subjects will receive standard surveillance and treatment for expectant management of EOP, which may include but is not limited to:

- Daily prenatal vitamin
- 24-hr urine collection for protein excretion at admission
- Blood sampling for hematologic, liver, and kidney function at time of diagnosis and every 2-3 days thereafter
- Magnesium sulfate for seizure prophylaxis
- Betamethasone to accelerate fetal lung maturity
- Antihypertensive agents
- Twice weekly fetal surveillance by NST (30 minutes of continuous fetal heart rate monitoring) or BPP (30 minutes of ultrasound to monitor for fetal breathing, movement, fluid)
- Weekly ultrasound to measure amniotic fluid and UA Dopplers

In addition to above standard care for EOP, subjects will receive surveillance and treatment solely for study purposes, including:

- Daily administration of vitamin B₃-amide, 2.5 Gm/day in 3 divided doses; "on treatment" is defined as within 24 hours of dose
- Daily (M-F) study staff visit to query side effects if in-patient; with each outpatient visit (typically twice a week) if discharged from the hospital
- Optional blood sampling to coincide with clinical blood draws to measure sFlt-1, nicotinamide and 2-pyridone levels; chart abstraction to review liver function testing results (done clinically)
- Chart abstraction for maternal and delivery data (up until maternal discharge) and neonatal data (until 30 days of age or until discharge, whichever occurs first). We will

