3.2 Study Outcomes

PRIMARY

- Maternal mean arterial blood pressure, defined as the highest MAP within 24 hour period

SECONDARY-SAFETY AND TOLERABILITY

- Liver toxicity, defined as 3x ULN of ALT or AST within 24 hours of study drug
- Maternal report of side effects
- Clinical parameters of maternal and fetal well being
- Composite neonatal outcome

Maternal or Fetal Parameter	Safety Endpoint
History	Headache unrelieved by oral analgesics
Physical examination	Abdominal tenderness, (right upper quadrant or epigastric)
Vaginal bleeding	Fall in hematocrit of $\geq 3\%$
Urine output	Oliguria (< 500 cc/24 hr)
Serum LFTs	AST and/or ALT $\geq 3x$ ULN within 24 hours of study drug
Fetal NST (or BPP)	Category III (or < 6)

SECONDARY-PHARMACOKINETICS

- Nicotinamide and metabolite concentrations in plasma at baseline, 2, 8, and 24 hours
- Peak plasma drug and metabolite concentration and time to reach peak
- Nicotinamide and metabolite elimination half-life
- Nicotinamide and metabolite area under the curve (integral of the plasma concentration-time curve)
- Nicotinamide and metabolite concentrations in urine at baseline, 8 and 24 hours

4 Subject Selection and Withdrawal

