4.4 Early Withdrawal of Subjects

4.4.1 When and How to Withdraw Subjects

Subjects may withdraw at any time and for any reason. Subjects may be withdrawn if they no longer meet eligibility criteria; or if in the opinion of the investigator it is not in the subject's best interest to continue. A subject may also be withdrawn if she experiences an unmanageable or irreversible adverse Grade 3 or 4 adverse event using the CTCA v3.0 criteria as defined in section on safety monitoring. The date of withdrawal from study participation will be recorded in the CRF. Subjects who either complete or are removed from the treatment phase at any time will have complete data chart abstracted and recorded for study purposes.

Specific study stopping rules include:

- Any maternal or fetal death deemed to be related or possibly related to study participation
- More than expected prevalence of liver toxicity within 24 hours of study drug, thus > 20% of subjects experience liver toxicity (more than 1 subject for every 5 subjects enrolled)
- More than expected prevalence of fetal side effects (defined as BPP < 6 OR UA Dopplers show absence or reversal of diastolic blood flow), (more than 1 delivery for fetal reasons per every 5 subjects enrolled)

Specific rules to stop study intervention for individual subject

- Delivery, or two weeks of treatment (“on-treatment” defined as within 24 hours of study drug)
- Liver toxicity (LFTs \geq 3x ULN within 24 hours of study drug)
- Maternal side effects that cannot be managed with oral medication

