8.1 Definitions

Unanticipated Problems Involving Risk to Subjects or Others

Any incident, experience, or outcome that meets all of the following criteria:

- Unexpected in nature, severity, or frequency (i.e. not described in study-related documents such as the IRB-approved protocol or consent form, the investigators brochure, etc)
- Related or possibly related to participation in the research (i.e. possibly related means there is a reasonable possibility that the incident experience, or outcome may have been caused by the procedures involved in the research,

Adverse Event

An **adverse event** (AE) is any symptom, sign, illness or experience that develops or worsens in severity during the course of the study. Intercurrent illnesses or injuries should be regarded as adverse events. Abnormal results of diagnostic procedures are considered to be adverse events if the abnormality:

- results in study withdrawal
- is associated with a serious adverse event
- is associated with clinical signs or symptoms
- leads to additional treatment or to further diagnostic tests
- is considered by the investigator to be of clinical significance

Adverse Event Grading

Adverse events will be graded using the Common Terminology for Criteria for Adverse Events (CTCAE) version 4.03 (published June 14, 2010).

Grade 1: Mild; asymptomatic or mild symptoms; clinical or diagnostic observations only; intervention not indicated; limiting. (e.g., GI distress, nausea, vomiting; flushing)

Grade 2: Moderate; minimal, local or noninvasive intervention indicated. (e.g. GI distress requiring IV therapy)

Grade 3: Severe or medically significant but no immediately life-threatening; hospitalization or prolongation of hospitalization indicated; disabling.

Grade 4: Life-threatening consequences; urgent intervention indicated.

Grade 5: Death related to AE.

Adverse Event Reporting Period

The study period during which adverse events must be reported is defined as the period from the initiation of any study procedures to the end of the study treatment follow-up. For this study, the study treatment follow-up for the mother is defined as until discharge from the hospital and the infant as until discharge or 30 days of life, whichever occurs first.

Preexisting Condition

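### The study-level death criterion covers maternal and fetal deaths but not a possibly related death of a live-born exposed infant, although the plan follows infants for safety

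*Combined protocol and SAP*

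**What the plan says.** Section 8.4 lists two circumstances that stop the study: "Any maternal or fetal death deemed to be related or possibly related to study participation", and ">20% subjects experience liver toxicity". Section 4.4.1 carries the same two criteria, the death criterion in identical words, and adds a third: "More than expected prevalence of fetal side effects (defined as BPP < 6 OR UA Dopplers show absence or reversal of diastolic blood flow". That third rule is counted as deliveries for fetal reasons, with a limit of one per five women enrolled.

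Elsewhere the infant is treated as a safety subject in its own right. Section 3.2 puts "Composite neonatal outcome" under safety and tolerability. Section 3.1 provides for neonatal chart abstraction and a phone call 30 days after delivery to ask about adverse events. Section 8.1 defines the adverse event follow-up for "the infant as until discharge or 30 days of life, whichever occurs first". Section 1.1 says that medically indicated preterm birth "contributes significantly to neonatal morbidity and mortality associated with preeclampsia".

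Section 8.6 says that the DSMB monitors against the pre-specified stopping rules and reviews data at each block of six enrolments. Between reviews it is notified of two kinds of event only: every second case of liver toxicity, and every second delivery in the first 48 hours on drug.

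**The concern.** Section 3.1 has dosing "continuing until delivery or 34 weeks, whichever occurs first". (Section 4.4.1 gives a two-week limit instead, which is a separate discrepancy.) On either text, an infant delivered during treatment has been exposed up to birth. The plan also monitors the fetus throughout, and 4.4.1 expects that some women will be delivered for fetal reasons. If a fetus deteriorates and is delivered alive but then dies, that death is neonatal. With the same relatedness judgement, it meets the death criterion if it happens before birth and does not if it happens after.

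This matters more here than in a controlled trial. The study is open label with no untreated preeclamptic group, so no comparison within the trial would show an excess of infant deaths. Section 1.4 says that pregnancy effects of pharmaceutical doses have not been studied, and reports a phase I study of only 10 women at lower doses. Pre-specified triggers and prompt notices to the board therefore carry much of the protection.

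**Working it through.** The plan states no figure to reproduce. The check sets the stopping lists beside the routes by which an infant death could reach someone able to act.

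**Step 1. The two lists.** Maternal or fetal death appears in 2 of 2 lists, and neonatal or infant death in 0 of 2. No definition extends fetal to the newborn, and the protocol uses fetal, neonatal and infant as separate terms.

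**Step 2. Three courses, each with a death judged at least possibly related.**

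| Course | Death criterion (4.4.1, 8.4) | Fetal-reasons rule (4.4.1 only) | DSMB notice between reviews (8.6) |
|---|---|---|---|
| Fetus dies in utero | Met | Not by the death itself | Not listed, but the study stops |
| Delivery for fetal reasons, infant later dies | Not met | The delivery counts as one event; the death adds nothing | Only through an early delivery, as one of two |
| Delivery for maternal reasons, infant later dies | Not met | Not counted | Only through an early delivery, as one of two |

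**Step 3. How much the fetal-reasons rule covers.** The limit is more than 1 delivery per 5 enrolled. At 5 women that takes 2 deliveries. Read cumulatively at 24 women (3.1 and 7.1), 24 ÷ 5 = 4.8, so it takes 5. At 25 women (Study Summary), 25 ÷ 5 = 5, so it takes 6. One delivery followed by an infant death does not reach the limit at any of these sizes, and 8.4 omits the rule.

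**Step 4. Reporting routes.**
- IRB (8.3): adverse events that are unexpected and related or possibly related. The post-study paragraph of 8.1 adds notice of deaths reasonably linked to the study after participation has ended.
- FDA (8.3.1): a 7-day report for unexpected fatal or life-threatening events associated with the agent.
- DSMB (8.6): the next six-subject review.

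The main IRB route and the FDA route require the event to be unexpected, which the stopping criterion does not. A preterm infant's death could be classed as expected while still being possibly related. None of these routes is a stopping trigger.

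**Step 5. The wait for a scheduled review.** There are 24 ÷ 6 = 4 reviews if only the preeclamptic women count. Assume even enrolment over the 24-month study duration in the Study Summary. Then 24 ÷ 24 = 1 woman a month, and six enrolments take about 6 months. If the 12 healthy women also count, 36 ÷ 24 = 1.5 a month, and the interval is 6 ÷ 1.5 = 4 months. A death just after a review could wait that long; quicker accrual shortens it. The protocol states no scheduled review after the last block of six.

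**The case against.** The strongest reply is that what is missing is an automatic trigger, not oversight. That is right, and it limits the point. A reader might infer that an infant death could pass with no review at all. The documents do not support this: infants are inside the adverse event period, there is a call 30 days after delivery, the IRB and FDA routes exist, the principal investigator regularly assesses serious adverse events (8.5), and the DSMB reviews data in blocks of six.

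A second reply is that collecting an outcome does not oblige a sponsor to stop on it. Headache, abdominal tenderness and oliguria are safety endpoints in 3.2 and are not study-stopping criteria. This also stands. Including infants in safety follow-up makes the omission worth explaining, but does not by itself make it an error.

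Third, the contrast with stillbirth must be drawn fairly. A stillbirth does not stop the study by itself; it must also be judged at least possibly related. The comparison holds only with that condition on both sides.

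Fourth, section 1.1 links neonatal death to indicated preterm birth. In an uncontrolled cohort enrolled at 24 weeks to 33 weeks 3 days, one such death may be hard to call unrelated, and 8.4 makes stopping mandatory. Adding infant deaths to that criterion could halt the study for prematurity alone. Fetal death shares some of this confounding, so the reply does not justify the present boundary. It does make a mandatory stop debatable.

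Finally, the DSMB charter is cited but not supplied, and may be broader. If so, the protocol's lists should agree with it.

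**Conclusion.** The point holds as a narrow gap in monitoring scope. A death of a live-born exposed infant judged related or possibly related meets no study-level death criterion in either list and requires no DSMB notice between reviews, while a fetal death with the same judgement stops the study. The fetal-reasons rule covers part of this, in one list only and only above its limit.

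The gap applies to every live-born infant of the 24 or 25 preeclamptic women from birth onward. Its practical size is a possible wait for the next scheduled review, about 4 to 6 months under the even-enrolment assumption, when the death is not reported sooner by another route. A reader might infer that most offspring deaths would fall outside the rule, because surveillance leads to delivery. The documents give neither death rates nor the split between fetal and neonatal deaths, so no such share can be stated.

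The conclusion rests on reading fetal in its ordinary sense and on the charter containing no wider rule.

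**What to change.** Reconcile the death criterion in 4.4.1 and 8.4 with the infant safety follow-up in 3.1, 3.2 and 8.1. Add to 8.6 that any infant death during follow-up judged related or possibly related is sent promptly to the DSMB, using the relatedness test already in the criterion. State the window this covers, because chart follow-up ends at the earlier of discharge and 30 days, while the phone call comes 30 days after delivery.

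The sponsor and DSMB should then state whether such a death also falls under the stopping criterion, and why. That choice is theirs; the notice is useful either way. The charter should be checked for consistency.

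The cost is a clarification in 4.4.1 and 8.4, a sentence in 8.6 and the charter check. Each infant death, including those from prematurity, will need a relatedness assessment, and some may prompt an unscheduled DSMB review. Sample size and analysis do not change.
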